4.7 External Beam Equipment and Beam Delivery

Protons: A 230 MeV proton beam will be used. Treatments will be administered in the Roberts Proton Therapy Center at the University of Pennsylvania. All charged particle treatment will be given with the patient in the appropriate immobilization device and aligned based on the departmental protocol.

Film or digital images will be taken prior to the initial treatment to verify the position of the patient and the aperture and as appropriate. A radiation oncologist will check the first film on all fields. A radiation therapist will check subsequent films taken before treatment.

All set-up films will be permanently filed for each subject.

4.8 Quality Assurance

4.1. Conventional portal filming

Daily portal films, and/or daily online radiographic imaging will be performed during therapy.

4.2. Video surface image guidance

Video surface image guidance will be used in all patients. Video surface mapping will be conducted with the AlignRT system (Varian Medical Systems, Palo Alto, CA). This system

employs dually mounted cameras that capture external surface anatomy. The data is used to generate 3D topographic mapping of the patient surface anatomy in the treatment set-up position. A region of interest, in this case the breast, can be used to reposition the patient or make shifts in couch position to improve daily set-up accuracy.

5 Systemic Therapy

5.1. Chemotherapy

Patients enrolled in this study will receive systemic therapy as deemed appropriate by their medical oncologist. If chemotherapy is recommended it will be given after radiotherapy but not concurrently. The interval between the RT and chemotherapy should be at least 2 weeks.

5.2 Endocrine Therapy

If endocrine therapy is recommended it may be initiated before, during, or after RT at the discretion of the patient's treating physicians.

6 Study Procedures

6.1 *Prior to study entry*

- History and Physical including breast exam and ECOG performance status.
- Breast MRI and/or Mammogram (or mammogram of right and left breast done at separate times) within six months of diagnosis.
- Negative post post-excision mammogram for patients with malignancy-associated calcifications after lumpectomy
- CBC within 6 months of study entry.
- AJCC TNM Staging.
- Serum Pregnancy test if applicable before radiation simulation.
- A treatment planning CT scan of the ipsilateral breast in the treatment position is required to define the clinical target volumes (CTV) and planning target volumes (PTV) for radiation. This should be done between 14 and 60 days after surgery.

CONFIDENTIAL

This material is the property of the University of Pennsylvania. Do not disclose or use except as authorized in writing by the study sponsor

6.2 Pre-treatment

- Patient reported health-related quality of life will be assessed using the Breast Cancer Treatment Outcomes Scale (BCTOS) (See Appendix for Scale)
- Physician reported Harvard cosmetic assessment (Excellent, Good, Fair, Poor)

6.3 Weekly During Treatment

- History and Physical including breast exam and ECOG performance status
- Physician toxicity assessment

6.4 Approximately one month after completion of radiation therapy, approximately 6 months after completion of RT, and then every approximately 6 months for 5 years' post-treatment

- History and Physical including breast exam and ECOG performance status
- Physician toxicity assessment
- Patient reported BCTOS
- Physician reported cosmetic assessment

Study Procedures

	Eligibility	Pre-treatment	Weekly	Months 1	Months 6, 12, 18, 24, 30, 36, 42, 48, 54, 60
Tests and Observations					
History and PE	X		X	X	X
ECOG performance status	X		X	X	X
Biopsy	X				
Pathology review	X				
ER/PR determination for invasive breast cancer	X				
Mammogram	X				Month 6 then annually
Laboratory					
CBC	X				
Pregnancy Test	X				
Toxicity Assessment			X	X	X
Patient-reported BCTOS		X		X	X
Physician cosmetic assessment		X		X	X

CONFIDENTIAL

This material is the property of the University of Pennsylvania. Do not disclose or use except as authorized in writing by the study sponsor

6.5 Post-treatment Evaluation and follow-up

- Patients will be treated and followed 1 month after completion of radiation treatment to determine feasibility and safety (acute toxicity).
- All subjects will be evaluated by a radiation oncologist 1 month after completion of RT. Additional time points at 6 months after completion of RT and every 6 months thereafter for a total of 5 years' post-treatment can be evaluated alternatively by surgery or medical oncology.
- For all follow-up time points, there is a window of +/- 2 months.
- Each follow-up examination will consist of interval history and physical examination including a breast exam and ECOG performance status and toxicity assessment.
- A bilateral mammogram will be obtained at month 6 and then annually.

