7.1 Feasibility Study

7.1.1 Design

A total of 12 patients will be enrolled. The total dose of 38.5 CGE will be given in 10 fractions. The regimen is intended to be completed in 5 treatment days. A fractionation schedule of 3.85 Gy once a day for 10 fractions over 2-3 weeks is also permitted. Patients undergo 2 fractions per day, a minimum of 6 hours apart. Twelve patients will be enrolled and followed for a minimum of 30 days after the completion of radiotherapy to score acute toxicity. This shortened follow-up period is appropriate for an accelerated treatment schedule in which treatment may be completed in 5 days. Thirty days of observation from the end of radiotherapy will be required in all 12 patients prior to commencing the phase II study. Patients enrolled in the feasibility study will continue to be followed beyond 30 days post-radiation, since they contribute to primary and secondary endpoints of the phase II study.

CONFIDENTIAL

This material is the property of the University of Pennsylvania. Do not disclose or use except as authorized in writing by the study sponsor

7.1.2 Objectives.

The primary objectives are to determine feasibility and the acute toxicity profile of accelerated partial breast radiation using protons. Additional objectives, such as late toxicities, cosmesis, and clinical efficacy are evaluated in these patients on the phase II portion of the trial.

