7.1.3 Endpoints

Primary Endpoints

Feasibility will be based on multiple radiation planning and treatment parameters. Should a patient experience one of the following events, treatment will be deemed infeasible:

- a) Patient cannot be given treatment because anatomy is such that a dosimetrically satisfactory treatment plan cannot be devised. For example, the dosimetry is unsatisfactory if < 95% of the target volume is covered by 95% of the dose.
- b) Patient is unable to tolerate more than 20% of treatments using proton radiotherapy (i.e., >2 of the 10 fractions). This can be for any reason, including the inability to set the patient up within acceptable limits of tolerance, or the patient is unable to tolerate treatment position or immobilization for duration of treatment. Thus, up to 20% (i.e., 2 of the 10 fractions) of treatments could be delivered using photons.
- c) Patient is unable to complete all treatment within 5 days of the estimated date of treatment completion or requires a treatment break of \geq than 5 days.
- d) No more than 20% of patients experience an acute toxicity, as defined below.

Acute toxicity is defined as any grade 3 or higher hematologic or non-hematologic toxicity, including skin changes, as graded by the NCI CTC Version 5.0, observed **within 30 days from the end of radiotherapy**, which is probably or definitely related to proton therapy.

Secondary Endpoints

Late toxicity is defined as any grade 3 or higher hematologic or non-hematologic toxicity which occurs more than 30 days after end of therapy. Late toxicities will be graded according to the CTC Version 5.0. Special attention will be paid to fibrosis and cosmesis. The time frame for late toxicity is open-ended because late toxicities have been known to occur a year or more after therapy. Follow-up for late toxicity will cease when a patient experiences disease progression since 2nd line therapies may then be initiated.

Cosmesis will be scored using the Harvard scoring system (scale = excellent, good, fair, poor) and CTC Version 5.0. In addition, cosmesis will be scored by the cosmesis and breast pain subscales of the Breast Cancer Treatment Outcomes Scale (BCTOS) instrument.

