Clinical Efficacy. Time to local failure will be defined as the time from the start of radiation therapy to local failure. Overall survival will be defined from the time from the start of radiation therapy to death due to any cause or last patient follow-up. These outcomes will likely be summarized during the phase II study.

7.1.4 Rules for Early Termination for Feasibility and Acute Toxicity.

Bayesian probability calculations will be employed to define rules of early termination for feasibility and safety. The tables below indicate termination rules after groups of 3 patients have been treated, although the Bayesian probability of an event may be calculated at any time during the trial. Hundreds of patients

with certain types of cancer have undergone radiation therapy with protons. Thus, we will assume a modest amount of “prior” feasibility and safety data for proton for our Bayesian calculations.

Feasibility

We will assume a beta (5,1) prior, which is information equivalent to feasibility established in 5 of 6 treated patients. A feasibility rate $\geq 90\%$ is considered acceptable. If the number of patients in whom proton is deemed feasible is less than or equal to the number in the table below then termination will be considered as it is highly unlikely that the feasibility rate is $> 90\%$, as noted by the Bayesian posterior probabilities.

Bayesian Rule for Feasibility				
Patients treated	3	6	9	12
Patients in whom proton is feasible	1	4	6	9
Posterior Prob[feasibility rate $> 90\%$]	0.04	0.09	0.04	0.08
Action	Terminate enrollment			

Acute Toxicity

Acute toxicity with accelerated partial breast radiotherapy with photons is quite low, although skin toxicity is fairly common. Proton therapy is expected to spare normal tissues; therefore, a rate of Grade 3 or higher acute toxicity observed **within 30 days from the end of radiotherapy**, including skin changes, which is probably or definitely related to proton therapy of $\leq 20\%$ is considered acceptable. We will assume a beta (1,5) prior, which is information equivalent to Grade 3 or higher acute toxicity in one of 6 treated patients. If the number of patients with Grade 3 or higher acute toxicity is greater than or equal to the number in the table below, then termination will be considered, because it is likely that the toxicity rate is $> 20\%$, as noted by the Bayesian posterior probabilities.

Bayesian Rule for Acute Toxicity including skin changes				
Patients treated	3	6	9	12

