Patients who experience acute toxicity	2	2	3	4
Posterior Prob [acute toxicity rate $> 20\%$]	0.80	0.62	0.70	0.76
Action	Terminate enrollment			

7.1.5 Statistical Analyses.

Feasibility: The posterior probability that this feasibility rate is 90% will be calculated. The feasibility rate and exact 90% CI will also be computed. The reasons why patients were not feasible will be tabulated.

Acute toxicity: All toxicities observed within 30 days from end of therapy will be graded by CTC Version 5.0 and tabulated. The posterior probability that this acute toxicity rate is 20% will be calculated.

Late toxicity: All toxicities observed later than 30 days from end of therapy will be graded by the CTC Version 5.0 and tabulated.

Cosmesis will be scored using the Harvard scoring system and CTC Version 5.0. BCTOS will be scored every 6 months and fold changes over time will be described and plotted.

Clinical efficacy: Local control (time to local failure) and overall survival will be estimated by the Kaplan-Meier method. It is likely that these time-to-event outcomes will be summarized after completion of the phase II study.

Estimation of Event Rates: The table below displays the 90% exact binomial confidence intervals based on 12 patients treated.

No. of Events	%	90% exact CI	No. of Events	%	90% exact CI
0	0.0	17.5*	7	58.3	31.5 , 81.9
1	8.3	.43 , 33.9	8	66.7	39.1 , 87.7
2	16.7	3.0 , 43.8	9	75.0	47.2 , 92.8
3	25.0	7.2 , 52.7	10	83.3	56.1 , 97.0
4	33.3	12.3 , 60.9	11	91.7	66.1 , 99.6
5	41.7	18.1 , 68.5	12	100.0	82.5*
6	50.0	24.5 , 75.5			* 90% 1-sided CI

7.2 PHASE II STUDY.

7.2.1 Design and Objectives.

Once feasibility and safety are established, then the phase II portion of the study will commence. A total of 57 patients will be enrolled; 12 patients are included from the feasibility study and 45 additional patients are enrolled in the phase II study. The two primary objectives are: to determine whether the rate of Grade 3+ acute toxicity is $\leq 20\%$ and whether the rate of maintained excellent to good cosmesis is $\geq 85\%$ at 2 years post-XRT. Only patients with excellent or good cosmesis at baseline contribute to this analysis.

7.2.2 Endpoints.

Acute Toxicity, as defined in Section 7.1.3

Cosmesis, as scored by the Harvard scale, CTC Version 5.0 and BCTOS scoring systems.

Late Toxicity, Local control and overall survival, as defined in Section 7.1.3

7.2.3 Rules for Early Termination for Acute Toxicity.

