7.3 SAMPLE SIZE/POWER

Acute toxicity. A total of 57 patients will be enrolled and will contribute to the hypothesis test of the acute toxicity rate. Since these are favorable risk patients, no loss to follow-up by 30 days post-XRT is expected. With 57 patients, there is 90% power for a chi-square test at a 1-sided 10% significance level, to test the null hypothesis that the acute toxicity rate is $\geq 35\%$ (clearly unacceptable) versus the alternative hypothesis that the acute toxicity rate is $\leq 20\%$. This analysis will be performed when 57 patients have 30 day post-XRT data.

Cosmesis at 2 years. The rate of excellent to good cosmesis on the Harvard scale will be scored at 2 years post-XRT. We anticipate that 3 patients will enroll on the study with fair cosmesis at baseline and they will be excluded from this endpoint. In addition, we anticipate that another 4 patients will be lost or have progressive disease before 2 years and who are not scored as fair or poor cosmesis (i.e., considered a failure) at a time point prior to 2 years and they will be excluded from this endpoint. Thus 50 patients will contribute to the analysis of whether excellent to good cosmesis is maintained at 2 years post-XRT. With 50 patients, there is 90% power for a chi-square test at a 1-sided 10% significance level, to test the null hypothesis that the cosmesis rate is $\leq 70\%$ (clearly unacceptable) versus the alternative hypothesis that the cosmesis rate is $\geq 85\%$.

7.4 TRIAL DURATION.

A total of 57 patients will be enrolled. With an expected monthly accrual of 2 patients, this study will enroll for approximately 2.5 years and the total duration of the study is approximately 4.5 years, in order to follow patients for 2 year cosmesis.

8 Safety and Adverse Events

The principal and secondary investigators will be responsible for detecting, documenting and reporting all events that meet the definition of an AE or SAE as defined in this protocol.

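### The ±2-month window on the month-1 visit does not fit a 30-day acute toxicity endpoint defined by when events are observed, so Grade 3+ events with onset by day 30 can drop out of the primary count

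*Combined protocol and SAP*

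**What the plan says.** **Visits.** Section 6.5 gives the 1-month follow-up its purpose: "Patients will be treated and followed 1 month after completion of radiation treatment to determine feasibility and safety (acute toxicity". The same section then sets one window for every visit: "For all follow-up time points, there is a window of +/- 2 months". Month 1 is not excepted. Section 6.4 lists the post-treatment assessments as "Approximately one month after completion of radiation therapy, approximately 6 months after completion of RT", then about every 6 months. The schedule table shows no toxicity assessment between month 1 and month 6.

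**Endpoint.** Section 7.1.3 defines acute toxicity as Grade 3+ toxicity, probably or definitely related to proton therapy, *observed* within 30 days from the end of RT. Section 7.2.2 carries this into phase II. Section 7.1.3 defines late toxicity as "any grade 3 or higher hematologic or non-hematologic toxicity which occurs more than 30 days after end of therapy". Section 7.1.5 words it differently: "All toxicities observed later than 30 days from end of therapy will be graded by the CTC Version 5.0 and tabulated". Section 7.2.4 says toxicities will be classed as acute or late but gives no rule for dating them.

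**Use.** For the gate to phase II, Section 7.1.1 says: "Thirty days of observation from the end of radiotherapy will be required in all 12 patients prior to commencing the phase II study". For the feasibility looks, Section 7.1.4 says: "The tables below indicate termination rules after groups of 3 patients have been treated". The phase II table in 7.2.3 is also indexed by patients treated. For the final test, Section 7.3 says: "This analysis will be performed when 57 patients have 30 day post-XRT data". It expects no loss to follow-up by day 30 and gives no rule for a patient who has no assessment near that day.

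**The concern.** A window of two months either side of a one-month visit is wider than the period that the visit is meant to describe. Two consequences follow.

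- **Late visit.** A visit on day 50 or day 75 complies with 6.5, yet the patient has had no scheduled examination between the end of RT and day 30. Whatever is found then was not observed within 30 days.
- **Early visit.** A visit on day 5 also complies with 6.5. The next scheduled toxicity assessment is month 6, which is itself ±2 months. This conflicts with the 30 days of follow-up in 7.1.1 and the 30-day data required in 7.3.

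On-treatment checks fill little of the gap. They are weekly, and a twice-daily course lasts 5 to 10 days (4.4.1), so such a patient may have only one or two.

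The acute toxicity rate is a primary endpoint. It feeds the gate to phase II, all the toxicity stopping tables and a formal hypothesis test. Apart from the 12-patient gate, the interim looks state no 30-day requirement, so a recently treated patient can count as event-free before any post-treatment assessment.

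**Working it through.** **1. Permitted visit dates.** Take one month as 365.25/12 = 30.44 days.

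- Latest month-1 visit: 3 × 30.44 = 91.3, about day 91.
- Earliest: 30.44 − 60.88 is negative, so the floor is the end of RT (day 0).
- Month-6 visit: months 4 to 8, about day 122 to day 243.

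**2. The definitions side by side.** Days are counted from the end of RT, for a related Grade 3 event.

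| Onset | First seen | Acute in 7.1.3 (observed by day 30) | Late in 7.1.3 (occurs after day 30) | Late in 7.1.5 (observed after day 30) |
|---|---|---|---|---|
| 25 | 28 | yes | no | no |
| 25 | 50 | no | no | yes |
| 40 | 50 | no | yes | yes |

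Only the second row is a problem. The event is out of the acute count under every wording, and the two sections disagree on whether it is late.

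**3. The plan's own figure (7.3).** The inputs are a null rate of 0.35, an alternative of 0.20, one-sided 10% significance, 90% power and N = 57.

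- n = [1.2816·√(0.35·0.65) + 1.2816·√(0.20·0.80)]² / 0.15² = 56.1, rounded up to 57. Power at 57 is 0.904, so the stated figure reproduces.
- Cutoff: 57·0.35 − 1.2816·√(57·0.35·0.65) = 15.34, so the test passes with 15 or fewer events.
- Check: 15/57 gives z = −1.375, p = 0.085. 16/57 gives z = −1.097, p = 0.136.
- Exact binomial: type I error 0.107, power 0.909.

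**4. Effect of uncounted events.** Let f be the share of true 30-day events that are not counted. The documents give no value, so f is assumed. At a true rate of 35% the counted rate is 0.35·(1 − f), and 57·0.35 = 19.95 events are expected.

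The final test alone passes with probability P(X ≤ 15) for X binomial(57, 0.35·(1 − f)). The last two columns apply the printed event counts as binding boundaries (2/3, 2/6, 3/9, 4/12, 6/20, 8/30, 10/40, 12/50), with the same f at every look.

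| f (assumed) | Counted rate | Expected uncounted | Final test alone passes | Some boundary crossed | Reaches and passes final test |
|---|---|---|---|---|---|
| 0 | 0.350 | 0 | 10.7% | 98.4% | 1.5% |
| 5% | 0.3325 | 1.0 | 16.6% | 97.3% | 2.7% |
| 10% | 0.315 | 2.0 | 24.5% | 95.4% | 4.5% |
| 20% | 0.280 | 4.0 | 45.5% | 88.9% | 11.1% |

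Termination at a boundary is only to be considered (7.1.4, 7.2.3). The last column is therefore the case of full adherence and the fourth the case where the looks play no part.

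**The case against.** The strongest reply is that the plan already protects the count.

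- **Recall and recording.** Section 6.5 includes an interval history at each follow-up, and 8.2 requires adverse events to be asked about at each contact and start dates to be recorded. A visit after day 30 can thus recover the onset of an earlier event. This stands, and it is why the effect may be zero. But no passage says that the start date decides the class, and the wording of 7.1.3 turns on observation.
- **Early visits.** Sections 7.1.1 and 7.3 can be read as excluding a visit before day 30 as the sole evidence. This stands for the 12-patient gate and the final test. It is still a conflict with 6.5 to reconcile, and it does not reach the other interim looks.
- **Stopping boundaries.** If followed, they remove most of the false-pass risk, as the last column of the table shows. This stands, with the caveat that they are not binding.

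Three stronger readings are tempting, but the documents do not support them.

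- A reader might infer that some events fall in no class at all. That is true only if 7.1.3 is read alone; 7.1.5 tabulates them as late.
- A reader might infer that events starting after day 30 could inflate the acute rate when found at a delayed month-1 visit. An event with onset on day 40 is late under both sections, wherever it is found.
- A reader might set the 60 days of acute toxicity assessment in 3.4.1 against the 30-day endpoint. That sentence directly follows one on subjects who have gone off study and most naturally concerns them.

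**Conclusion.** The point holds in a limited form. The visit window in 6.5 does not fit the 30-day endpoint, and 7.1.3 and 7.1.5 use different words for the same boundary. The error runs one way, toward too few acute events and so toward passing.

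Its size cannot be known from the documents. It is zero if visits cluster just after day 30, or if onset dates are well taken and used to classify events. With 5% to 20% of events uncounted at a true 35% rate, the final test alone passes with probability 16.6% to 45.5%, against 10.7% with none uncounted. With all boundaries followed, the range is 2.7% to 11.1%, against 1.5%. Both ranges rest on the assumed share, and the 45.5% should not be quoted without its companion figure.

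This should be fixed because the mismatch is plain in the text and the repair is cheap, not because harm has been shown.

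**What to change.** Keep the 30-day endpoint, N = 57, the cutoff of 15 and the stopping thresholds.

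- **Section 6.5.** For the month-1 visit alone, replace ±2 months with a narrow window just after day 30, for example days 30 to 35 after the end of RT.
- **Sections 7.1.3, 7.1.4 and 7.1.5.** Class toxicity as acute or late by the recorded date on which Grade 3 is first reached (on or before day 30, or after it), whenever it is seen.
- **Sections 7.1.4, 7.2.3 and 7.3.** Count a patient as event-free at a look or in the final test only after that assessment. Count a known Grade 3+ acute event at once. If the assessment is missed, classify from the next contact by onset date and report how many patients were handled this way.

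The cost is amendment wording and tighter scheduling of one existing visit. Each look also waits about 35 days after its last patient finishes RT. In that time about 2 more patients enrol at the 2 per month of Section 7.4 (2 × 35/30.44 = 2.3), or about 1 at the 10 to 12 per year of Section 3.3 (0.96 to 1.15).
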